
Statistical methods:
 
Justification of sample size
 
The study will randomize 200 patients. Given the possible non-inclusion of patients at the screening stage, the maximum number of patients to sign the Informed Consent Form in the Patient Information Leaflet and to participate in screening will be no more than 210 people.
 
At the first stage, 40 patients are included in each study arm and the most sensitive efficacy criterion of the two selected is determined, or additional analysis is carried out to select the criterion from secondary ones. Given 40 patients in each of the study arms, the sensitivity of the study to confirm 15% superiority by incidence, supposing the expected response 80% in the test drug arm, will exceed 45%.
 
Two Independent Proportions (Null Case) Power
 
Analysis
 
Numeric Results of Tests Based on the Difference: P1 - P2 H0: P1 - P2 ≥ 0. H1: P1 - P2 = D1 < 0. Test Statistic: Z test with pooled variance
 
  
 	Sample Size Grp 1	Sample Size Grp 2	Prop H1 Grp 1 or Trtmnt P1	Prop Grp 2 or Control P2	Diff if H0 D0	Diff if H1 D1	Target Alpha	Actu Alpha	
   
 Power	0.4553	40	40	0.6500	0.8000	0.0000	-0.1500	0.0500	0.0500	
  
				Sample Size Grp 1	Sample Size Grp 2	Prop H1 Grp 1 or Trtmnt P1	Prop Grp 2 or Control P2	Diff if H0 D0	Diff if H1 D1	Target Alpha	Actu Alpha	Power	0.4553	40	40	0.6500	0.8000	0.0000	-0.1500	0.0500	0.0500
	Sample Size Grp 1	Sample Size Grp 2	Prop H1 Grp 1 or Trtmnt P1	Prop Grp 2 or Control P2	Diff if H0 D0	Diff if H1 D1	Target Alpha	Actu Alpha													
Power	0.4553	40	40	0.6500	0.8000	0.0000	-0.1500	0.0500	0.0500												

Sponsor: PROMOMED RUS LLC, Russia	Separate study table relating to part of the dossier	(For use by national authorized bodies only)
Name of finished product: Areplivir, film-coated tablets	Volume: Pages:	
Active ingredient: Favipiravir		

Said statistical power (45%) is acceptable for exploratory stages of the studies aimed to select the duration for endpoint monitoring and to select the endpoint at the second (confirming) stage.

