
Certified statistical software with validated algorithms is used to perform statistical analyses and to ensure proper documenting (StatSoft Statistica 10.0., IBM SPSS Statistics 22).
 
Descriptive statistics are provided for all efficacy and safety indicators collected during the study. Continuous (quantitative) data are presented using the number of observations, arithmetic mean value, confidence interval (CI) 95% for mean, standard (rms) deviation, median, interquartile span (25th and 75th centiles), minimum and maximum.
 
Ordinal, categorical and qualitative data are presented as absolute frequencies (number of observations), relative frequencies (percent) and 95% CI (unless otherwise stated).
 
The check for normality of distribution is carried out by one of the generally accepted methods (Shapiro-Wilk test, Kolmogorov-Smirnov test). For non-Gaussian distributions, non-parametric methods will be used to compare efficacy and safety indicators.
 
Significance levels and confidence intervals are calculated as bilateral, the statistical significance of differences is two-sided by default and refers to significance level 0.05 (unless specified otherwise).
 
Analysis of demographics and other source data
 
Demographic data (age, sex) and baseline condition data are presented along with summaries in the form of absolute frequencies (number of observations), relative frequencies (percent), or using the arithmetic mean, confidence interval (CI) 95% for mean, standard deviation, median, interquartile span (25th and 75th centiles), minimum and maximum, depending on the type of variable.
 
To test the study group homogeneity hypothesis, at the baseline zero hypotheses (no differences between groups) are tested with Student's t-test (for interval measures with normal distribution in the study population), Mann-Whitney's test (for ordinary measures or for interval measures with distribution different from normal) or Fisher's exact test and χ^2 test (for qualitative indicators). If statistically significant differences between study arms are found, the magnitude of differences is estimated using confidence intervals.
 
Analysis of primary efficacy parameter
 
Primary efficacy endpoints:
 
One of the primary efficacy parameters is the time (in days) to improvement of patient's clinical status according to the categorical ordinal scale of clinical improvement.
 
 • Time (in days) to improvement in clinical status on a categorical ordinal scale of clinical improvement. 
To compare the primary efficacy indicator between arms, the Student's t-test for independent samples is used. If the necessary assumptions about the normality of distribution of this indicator are not met, the non-parametric Mann-Whitney test will be used. Also, the Kaplan-Meier technique and compilation survival tables can be used as descriptive methods for studying this efficiency parameter. Gehan-Wilcoxon test, Cox-Mentel test or Log-Rank test can be used to compare the time (in days) to improve the clinical status of the patient between the study groups.
		

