- Incidence of serious adverse events (SAEs) associated with the use of the study drug/standard therapy;
- Percentage of patients with at least one AE;
- Percentage of patients who discontinuation treatment due to AE.

Cross-group comparisons are performed for all safety indicators. The comparison of groups on frequency indicators is carried out using the *Fischer's exact test* or the χ^2 (chi-square) test, depending on the expected value in the cells of contingency table. For quantitative laboratory results, comparisons between groups at relevant visits are made using the *Student's t-test* or the *Mann-Whitney test* (depending on the nature of the distribution of quantitative indicators).

For analysis of all safety parameters the safety population was used.

In case of developing acute respiratory distress syndrome and the need to switch patient to mechanical ventilation, the investigational drug is canceled, but the patient is not withdrawn from the study. Patients are under follow-up until Visit 6, the data are taken into account to assess efficacy in the ITT population.

Interim analysis

In the first stage, 40 patients were included in each group (study arm). Given 40 patients in each of the study arms, the sensitivity of the study to confirm 15% superiority by incidence, supposing the expected response 80% in the test drug arm, will exceed 45%.

Sponsor: PROMOMED RUS LLC, Russia	Separate study table relating to part of the dossier	(For use by national authorized bodies only)
Name of finished product: Areplivir, film-coated tablets	Volume: Pages:	
Active ingredient: Favipiravir		

Two Independent Proportions (Null Case) Power Analysis									
Numeric Results of Tests Based on the Difference: P1 - P2									
H0: P1 - P2 ≥ 0. H1: P1 - P2 = D1 < 0. Test Statistic: Z test with pooled variance									
		Sample Size	Sample Size	Prop H1	Prop				
		Grp 1	Grp 2	Grp 1 or	Grp 2 or	Diff	Diff	Target	Actu
	Power	N1	N2	Trtmnt	Control	if H0	if H1	Alpha	Alpha
				P1	P2	D0	D1		
	0.4553	40	40	0.6500	0.8000	0.0000	-0.1500	0.0500	0.0500

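### The stage 1 power of over 45% is that of a one-sided 5% test; the two-sided test planned for the Visit 3 rate has about 32%

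*Combined protocol and SAP*

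**What the plan says.** All references are to the combined protocol and SAP, section 2, Overview (Synopsis), Statistical methods.

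- **Justification of sample size.** The design is stated as follows: "At the first stage, 40 patients are included in each study arm". The claim is that "the sensitivity of the study to confirm 15% superiority by incidence, supposing the expected response 80% in the test drug arm, will exceed 45" per cent. The software output beneath it has the row "0.4553 40 40 0.6500 0.8000" (power, the two group sizes, the two rates), with a target and actual alpha of 0.05. Its null hypothesis is P1 - P2 ≥ 0, and its header continues "H1: P1 - P2 = D1 < 0. Test Statistic: Z test with pooled variance". The figure is then called acceptable: "Said statistical power (45%) is acceptable for exploratory stages of the studies aimed to select the duration for endpoint monitoring".
- **Interim analysis.** The same claim, output and remark on acceptability appear again.
- **General methods of analysis**, repeated under **Significance level used in the clinical study.** The default is that "the statistical significance of differences is two-sided by default and refers to significance level 0.05 (unless specified otherwise".
- **Analysis of primary efficacy parameter.** The rate of improvement by two or more categories at Visit 3 is compared by a two-sided Fisher's exact test, or by a two-sided chi-square test when all expected cell counts are at least 5. The level is 5%.

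**The concern.** The power output has a directional null and a directional alternative, and it spends the whole 5% in one tail. The analysis section splits the 5% between two tails for the same endpoint. A power figure describes the test it was computed for, so the claim that sensitivity will exceed 45% may not hold for the test the plan specifies.

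At stake is the reason given for 40 patients per arm. The plan offers this one figure, judges it acceptable for choosing the endpoint of the confirmatory stage, and states it in two places. A reader deciding whether 40 per arm is enough for that purpose should be given the power of the planned test.

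**Working it through.** **Inputs** (all from the synopsis): n = 40 per arm; 65% versus 80%, a difference of 0.15; alpha 0.05; pooled Z test. The pooled Z test is equivalent to the uncorrected chi-square test when used two-sided. Critical values are 1.645 one-sided and 1.960 two-sided.

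**Step 1. Reproduce the plan's figure.** Exact power is the sum, over all pairs (x, y) from 0 to 40, of Bin(x; 40, 0.65) × Bin(y; 40, 0.80), counting the pairs for which the pooled statistic z = (y/40 - x/40) / √(2·p̄(1 - p̄)/40), with p̄ = (x + y)/80, exceeds the critical value.

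- One-sided, z > 1.645: **0.4553**, the printed figure to four decimals.

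Normal approximation as a cross-check:

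- Standard error under the null: √(2 × 0.725 × 0.275 / 40) = 0.0998.
- Standard error under the alternative: √((0.65 × 0.35 + 0.80 × 0.20) / 40) = √(0.3875/40) = 0.0984.
- One-sided power: Φ((0.15 - 1.645 × 0.0998) / 0.0984) = Φ(-0.145) = 0.443, close to the exact value.

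No two-sided variant that was tried reproduces 0.4553.

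**Step 2. Apply the planned two-sided test.**

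| Calculation, 40 per arm, 65% vs 80%, two-sided 5% | Power |
|---|---|
| Chi-square (pooled Z), exact enumeration | **0.322** |
| Plan's rule for choosing chi-square or Fisher, exact | 0.322 |
| Pooled normal approximation: Φ((0.15 - 1.960 × 0.0998) / 0.0984) = Φ(-0.464) | 0.321 |
| Unpooled normal approximation: Φ(0.15/0.0984 - 1.960) = Φ(-0.436) | 0.331 |
| Unpooled Z, exact enumeration | 0.338 |

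The gap is 0.4553 - 0.322 = 0.133, about 13 percentage points.

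**Step 3. Which of the two tests applies?** The expected number of non-responders per arm is about 40 × (1 - 0.725) = 11, well above 5. At these rates the plan's rule selects chi-square with probability 0.9997, so chi-square sets the power. Fisher's exact test used throughout would give 0.245, but the plan does not call for that here.

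**Step 4. Does another control rate restore the 45%?** The sample size text also mentions a 70% response on standard therapy, although both calculations use 65%. Exact two-sided power is 0.366 for 70% versus 85%, and 0.177 for 70% versus 80%. Neither reaches 45%.

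**Step 5. The full-study calculation.** It has the same directional hypotheses, with an unpooled Z test. Power is Φ(0.15 / √(0.3875/n) - critical value).

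- 107 per arm: 0.15/0.0602 = 2.493. One-sided Φ(0.848) = 0.8017, the printed 0.80170. Two-sided Φ(0.533) = 0.703.
- 100 per arm, the number planned: 0.15/0.0622 = 2.410. One-sided Φ(0.765) = 0.778. Two-sided Φ(0.450) = 0.674.

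**The case against.** The arithmetic in the table is right for the test it names, and the directional hypotheses are printed openly. The two-sided rule is only a default that allows exceptions, and the plan names no significance test by which the stage 1 endpoint is to be chosen. Stage 1 is labelled exploratory, no minimum power is set for it, and the plan has no statistical stopping criteria. Both 45% and 32% are far below a confirmatory level. The synopsis also describes an interim report on 80 patients, so a restated power will not change stage 1 enrolment. The more consequential instance is the full-study calculation.

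Most of this stands as a limit on the consequence. It does not remove the mismatch. The analysis section says two-sided at 5% for this very endpoint, and a hypothesis line in software output does not set an analysis rule. No text makes stage 1 an exception.

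Three stronger readings are tempting, and the documents do not support them.

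- *A reader might infer that the endpoint choice rests on noisier data than stated.* Sidedness moves the rejection threshold, not the data. The standard error of the difference is about 9.8 points under either test.
- *A reader might infer that an endpoint could be dropped for a non-significant stage 1 result.* The plan asks which endpoint is most sensitive and states no such rule. The 45% also concerns only the binary endpoint, so it never measured how reliable the selection is.
- *A reader might take the shortfall as 21 points, using Fisher's exact test.* The plan's own rule almost always selects chi-square at these rates.

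**Conclusion.** The point holds as an inconsistency between the basis of the power figure and the planned test. The claim that sensitivity will exceed 45% is not true of the two-sided 5% chi-square test specified for the Visit 3 rate. That test has about 32% power under the plan's own inputs (40 per arm, 65% versus 80%, no dropout). The range is 32% to 34% across the pooled and unpooled calculations, and about 37% if the rates were 70% and 85%.

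The consequence is limited to the stated justification for 40 per arm. It does not touch the precision of the stage 1 data, and it does not by itself undermine a confirmatory conclusion. The same one-sided basis lowers the full-study figure from 0.80 to about 0.70 at 107 per arm, and gives about 0.67 at the planned 100 per arm. That instance carries more weight, and the two should be handled together.

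**What to change.** 1. Under Justification of sample size and under Interim analysis, restate the stage 1 power as about 32% for the two-sided 5% chi-square test (40 per arm, 65% versus 80%). Alternatively, keep 45%, label it explicitly as one-sided 5%, and print 32% beside it.
2. In both places, make the sentence that calls the power acceptable refer to the corrected figure, and confirm that the judgement still holds for an exploratory stage.
3. Put the full-study calculation on the same two-sided basis in the same revision.

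For stage 1 the cost is a less favourable number in two paragraphs, with no change to patient numbers, procedures or analysis. That statement does not extend to the full study, where the two-sided power at 100 per arm has to be considered on its own merits.

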In case change of the planned endpoints, separate adjustment will be made for the multiplicity of comparisons and the required number will be recalculated at the second stage.

The total planned number of patients before the completion of the first stage will be 100 patients in each of the arms.

The estimated calculation until the data of the first stage are obtained is as follows. Given the available data from Chinese researchers, 15% superiority of favipiravir therapy over standard therapy without favipiravir is allowed in relation to the rate of improvement by 2 or more categories on categorical scale by day 10 of treatment. The adopted higher response to standard therapy of 70% is associated with a longer duration relative to the Chinese study (10 days instead of 7 days).

An RCT enrolling patients within 12 days of symptom onset found that favipiravir was superior to arbidol in terms of the clinical recovery rate at day 7 in patients with mild illness (62 [56%] of 111 with arbidol vs 70 [71%] of 98 with favipiravir), but not in those with critical illness (0 vs 1 [6%]). (Chen C. Huang J. Cheng Z. et al. Favipiravir versus arbidol for COVID-19: a randomized clinical trial. medRxiv. 2020; (published online April 15.) (preprint).

Tests for Two Proportions

Numeric Results for Testing Two Proportions using the Z-Test with Unpooled Variance

H0: $P_1 - P_2 \geq 0$ vs. H1: $P_1 - P_2 = D_1 < 0$.

Target	Actual	Diff						
Power	Power*	N1	N2	N	P1	P2	D1	Alpha
0.80170	107	107	214	0.6500	0.8000	-0.1500	0.0500	0.80

* Power was computed using the normal approximation method.

Thus, the minimum number of subjects required for a clinical study is 200 with 100 subjects randomized to each of the two groups.

Statistical analysis

The purpose of statistical analysis is to prove superiority of Areplivir, film-coated tablets (PROMOMED RUS LLC, Russia), over standard therapy in patients hospitalized with COVID-19.

The results of statistical analysis, descriptive statistics and illustrative tables, graphs, lists will be presented in interim and final clinical study reports.

General methods of analysis

Statistical analysis is carried out in accordance with the requirements of the Guideline for Good Clinical Practice (ICH 9) approved by the Eurasian Economic Commission, and other applicable requirements and laws.

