
Sponsor: PROMOMED RUS LLC, Russia	Separate study table relating to part of the dossier	(For use by national authorized bodies only)
Name of finished product: Areplivir, film-coated tablets	Volume: Pages:	
Active ingredient: Favipiravir		

The proof of the superiority hypothesis is the establishment of a statistically significant time difference (in days) before patient's clinical status improvement between the Areplivir arm and the standard therapy arm.

The next primary efficacy parameter is the percentage of patients who achieved an improvement in clinical status according to the categorical ordinal scale of clinical improvement by 2 or more categories at Visit 3.

- Rate of clinical status improvement by categorical ordinal scale of clinical status improvement by 2 or more categories at Visit 3.

For the analysis of this parameter, an intergroup comparison of percentages is used using a two-sided version of the **Fischer's exact test** (or a two-sided version of the χ^2 (chi-square) test, if all the expected values in the cells of the contingency table for this analysis are 5 or more). The percentage of patients who achieved improvement in clinical status on a categorical ordinal clinical improvement scale by 2 or more categories at Visit 3 is presented with a two-sided 95% confidence interval by treatment arm. Hypothesis testing is performed at a 5% significance level. The difference in proportion between treatment arms and the 95% bilateral confidence interval for the difference in proportion calculated by **Newcomb-Wilson technique is presented**.

The proof of the hypothesis of superiority of Areplivir film-coated tablets (PROMOMED RUS LLC, Russia) is the establishment of a statistically significant difference in the proportions of patients who achieved an improvement in clinical status according to the categorical ordinal scale of clinical improvement by 2 or more categories at Visit 3, between Areplivir arm and standard therapy arm.

Analysis of the primary efficacy parameter is performed in the ITT population (main analysis), and in the PP population (additional analysis). A summary of all efficacy indicators is provided.

Analysis of secondary efficacy parameters

The following efficacy parameters in the protocol are represented by qualitative values:

- Percentage of patients with elimination * COVID-19 according to PCR analysis at Visit 3.
- Percentage of patients transferred to intensive care unit.

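### Visit 3 improvement rate: the sample size rests on a one-sided 5% calculation that needs 107 per arm, but the plan takes 100 per arm and tests two-sided, so power is about 67% to 73%, not 80%

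*Combined protocol and SAP*

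**What the plan says.** All references are to the combined protocol and SAP, section 2 (Synopsis), under Statistical methods.

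- **Size.** In the justification of sample size, the second power table uses a Z test with unpooled variance, a one-directional alternative (P1 − P2 < 0), alpha 0.05, rates of 65% and 80%, and a power target of 0.80. Its answer is 107 per arm, 214 in total, with actual power 0.80170. The next sentence reads: "Thus, the minimum number of subjects required for a clinical study is 200 with 100 subjects randomized to each of the two groups".
- **Assumed rates.** The text above that table says "15% superiority of favipiravir therapy over standard therapy without favipiravir is allowed" for improvement by day 10, and "The adopted higher response to standard therapy of 70% is associated with a longer duration relative to the Chinese study". The stage 1 paragraph relies on "supposing the expected response 80% in the test drug arm, will exceed 45" percent power.
- **Stage 1 table.** With 40 per arm at 65% versus 80% it prints power 0.4553, under the line "H1: P1 - P2 = D1 < 0. Test Statistic: Z test with pooled variance".
- **Analysis.** For the Visit 3 rate, the section on the primary efficacy parameter says "For the analysis of this parameter, an intergroup comparison of percentages is used using a two-sided version of the" Fisher exact test, or a two-sided chi-square test when all expected cell counts are at least 5. It adds "Hypothesis testing is performed at a 5% significance level". The general methods also make two-sided 0.05 the default.
- **Recalculation.** If the planned endpoints change, "the required number will be recalculated at the second stage".

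**The concern.** Three things do not fit together.

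1. The size was worked out for a one-sided test at 5%, but the analysis is a two-sided test at 5%. This is the main problem.
2. The table asks for 214 patients and the sentence that draws on it calls 200 the minimum.
3. The text adopts 70% on standard therapy with a 15-point gain, which implies 85% on the test drug. The table uses 65% and 80%, and the stage 1 text also expects 80% on the test drug. The basis for 200 therefore cannot be identified.

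The stated purpose of the analysis is to prove superiority. A reader who sees 200 called the required minimum, beside a table with an 80% target, will take the risk of missing the assumed effect to be about 20%. If it is nearer 27% to 33%, a neutral Visit 3 result carries less weight than the plan suggests. The documents give no power calculation for the other primary criterion, time to improvement, so this point covers the Visit 3 rate only.

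**Working it through.** **Inputs.** From the sample-size text and tables: 65% versus 80%; 70% control with a 15-point gain (70% versus 85%; the 85% is inferred, not printed); 107 and 100 per arm; alpha 0.05. From the primary analysis section: a two-sided test at 5%. Critical values are 1.645 (one-sided) and 1.960 (two-sided). No dropout allowance is stated and none is applied.

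**Formulas** (unpooled Z, as in the plan's table; Φ is the standard normal distribution function):

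- SE = √{[p1(1−p1) + p2(1−p2)]/n}
- power = Φ(d/SE − z_α)
- n per arm = [p1(1−p1) + p2(1−p2)] × [(z_α + 0.842)/d]²

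**Step 1: reproduce the plan's figure.** At 65% versus 80% the variance sum is 0.2275 + 0.1600 = 0.3875.

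- One-sided n = 0.3875 × (2.486/0.15)² = 106.5, rounded up to 107.
- At n = 107, SE = 0.0602 and d/SE = 2.493. One-sided power is Φ(2.493 − 1.645) = 0.8017, the printed value.
- Two-sided, the same 107 gives Φ(2.493 − 1.960) = 0.7028.

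The table is therefore one-sided in its arithmetic as well as in its stated hypotheses.

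**Step 2: 100 per arm at 65% versus 80%.** SE = 0.06225 and d/SE = 2.410.

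- One-sided: Φ(0.765) = 0.778. Moving from 107 to 100 costs 80.2 − 77.8 = 2.4 points.
- Two-sided: Φ(0.450) = 0.674. Sidedness costs a further 77.8 − 67.4 = 10.4 points.

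**Step 3: 100 per arm at 70% versus 85%.** The variance sum is 0.2100 + 0.1275 = 0.3375, SE = 0.0581 and d/SE = 2.582.

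- One-sided: Φ(0.937) = 0.826. Here 93 per arm would be enough (n = 92.7).
- Two-sided: Φ(0.622) = 0.733.

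The rate conflict does not lower power by itself. But 100 per arm is adequate only by combining rates that are not in the table with a test that is not planned.

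**Step 4: check against other methods.** Two-sided 5%, 100 per arm; the exact column enumerates the planned chi-square/Fisher rule.

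| Rates | Unpooled Z | Pooled Z | Exact |
|---|---|---|---|
| 65% v 80% | 67.4% | 66.3% | 66.6% |
| 70% v 85% | 73.3% | 72.2% | 72.9% |
| 70% v 80% | 37.6% | 37.1% | 37.1% |

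The choice of method moves the answer by about one point. The last row takes the printed 70% and 80% literally. It contradicts the stated 15-point effect, so it shows only that the rates need reconciling.

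**Step 5: what 100 per arm can detect.** Two-sided 80% power needs a difference of 17.1 to 17.3 points from a 65% control rate, or 16.1 to 16.3 points from 70%. For reference only, 80% power for a 15-point difference would need 136 to 138 per arm (65% v 80%) or 118 to 121 (70% v 85%).

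**Step 6: stage 1.** At 40 per arm and 65% versus 80%, exact enumeration of the one-sided pooled Z test gives 0.4553, the printed figure. The planned two-sided rule gives 0.322.

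**The case against.** The arithmetic is hard to contest, and no exception to two-sided testing covers this endpoint, because its own analysis paragraph names a two-sided test. The best counter-arguments are about weight.

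- **The number is provisional.** The plan calls the calculation estimated until stage 1 data are available, and stage 1 may keep or replace the endpoint. This softens the point without curing it. Recalculation is conditional on a change of planned endpoints, so nothing triggers it if the Visit 3 rate is kept. Whether narrowing two primary criteria to one counts as a change is undefined. Even if it does, the sidedness of the recalculation is not stated, so the same mismatch could recur.
- **The error rate and analysis do not change, and a confidence interval will be reported.** True, and the interval for the difference will show the imprecision. It does not make the stated basis for 200 correct.
- **The plan never says that 100 per arm gives 80%.** True literally. But 200 is presented as following from a table with an 80% target.
- **70% versus 85% is inferred.** This stands, and the 73% figure must carry that label. The fully printed pair gives the lower figure, 67%.
- **The cited external data do not yield either control rate.** This also stands. They are day 7 recovery rates of 56% and 71% in mild illness, so the chosen pair will remain partly an assumption.
- **Stage 1 is exploratory and its table already shows the one-directional hypothesis.** Fair. No test is stated for the stage 1 selection, so the 32% is conditional and this item is minor.

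**Conclusion.** The concern holds. For the Visit 3 improvement rate, the plan derives a minimum of 200 from a calculation that requires 214 and that assumes a one-sided test the plan does not use. At 100 per arm, the planned two-sided 5% test has about 67% power at 65% versus 80%, and about 73% at 70% versus 85%. The chance of missing the assumed 15-point effect is thus about 27% to 33%, not 20%. Sidedness accounts for about 10 to 11 points of the shortfall at 65% versus 80%, and the cut from 107 to 100 for 2.4.

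These figures assume the stated 15-point effect, complete data on 100 per arm, and no multiplicity adjustment. They concern this endpoint only and do not affect its false-positive rate. The statement is wrong as written and must be corrected.

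**What to change.** 1. Reconcile the control and test-arm rates to one pair and use it in both text and tables. Justify it from the pre-trial external data already cited, say openly which part is assumption, and do not draw on the stage 1 results: the synopsis already reports on 80 patients.
2. State the power of the planned two-sided 5% test at 100 per arm: about 67% if the pair is 65% and 80%, or about 73% if it is 70% and 85%.
3. Remove the claim that a minimum of 200 follows from the table giving 214.
4. Specify that any second-stage recalculation uses the planned two-sided 5% test.
5. Label the stage 1 figure of 45% as one-sided, and add that it is about 32% if the two-sided 5% test is applied.

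The cost is protocol and SAP wording, and a less favourable stated power. This correction does not require more patients.
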